## Statistical Analysis Plan

Sponsor Name: Golden Biotechnology Corporation  
Sponsor Protocol ID: GH Covid-2-001

Covance Study ID: 000000203201

**CONFIDENTIAL**

Document Date: 29 Nov 2021

Page 2 of 34  
ST-AD-008 version 05

**CONFIDENTIAL**

Document Date: 29 Nov 2021

Page 3 of 34  
ST-AD-008 version 05

## Statistical Analysis Plan

Sponsor Name: Golden Biotechnology Corporation  
Sponsor Protocol ID: GH Covid-2-001

Covance Study ID: 000000203201

**CONFIDENTIAL**

Document Date: 29 Nov 2021

Page 4 of 34  
ST-AD-008 version 05

**Statistical Analysis Plan**

Sponsor Name: Golden Biotechnology Corporation

Sponsor Protocol ID: GH Covid-2-001

Covance Study ID: 000000203201

**Glossary of Abbreviations**

Abbreviation	Term
AE	Adverse Event
ANOVA	Analysis of variance
AUC	area under the plasma concentration versus time curve
AUC 0-last	area under the plasma concentration versus time curve from time zero to the time of last quantifiable concentration
AUC tau	area under the plasma concentration versus time curve within a dosing interval
BMI	Body Mass Index
BID	twice daily
BLQ	below the level of quantification
BOR	Best Overall Response
CI	Confidence Interval
CT	computerized tomography
CV	Coefficient of Variance
C max	maximum plasma concentration
COVID-19	Coronavirus Disease 2019
C trough	trough (predose) plasma concentration
DCR	Disease Control Rate
DOOR	Duration of Response
DMC	Data Monitoring Committee
ECG	Electrocardiogram
ECMO	extracorporeal membrane oxygenation
EOS	End of Study
ET	Early Termination
eCRF	Electronic Case report form
ICF	Informed Consent Form
ICU	intensive care unit
ITT	intention-to-treat
LDL-C	Low Density Lipoprotein-Cholesterol
LLOQ	the lower limit of quantification
KM	Kaplan-Meier
MedDRA	Medical Dictionary for Regulatory Activities
NC	not calculated
mITT	modified intention-to-treat
PK	Pharmacokinetics
PKS	Pharmacokinetic Set
PPS	Per Protocol Set
PT	Preferred Term
QTcB	Bazett corrected QT interval
QTcF	Fridericia corrected QT interval
SAE	Serious Adverse Event
SAP	Statistical Analysis Plan
SD	Standard Deviation
SOC	System Organ Class
SoC	Standard of Care
SS	Safety Set
TEAE	Treatment Emergent Adverse Event
TFLs	Tables, Figures and Listings

**CONFIDENTIAL**

Document Date: 29 Nov 2021

Page 5 of 34  
ST-AD-008 version 05

## Statistical Analysis Plan

Sponsor Name: Golden Biotechnology Corporation

Sponsor Protocol ID: GH Covid-2-001

Covance Study ID: 000000203201

$t_{max}$	Time to $C_{max}$
WHO	World Health Organization

**CONFIDENTIAL**

Document Date: 29 Nov 2021

Page 6 of 34  
ST-AD-008 version 05

## Statistical Analysis Plan

Sponsor Name: Golden Biotechnology Corporation

Sponsor Protocol ID: GH Covid-2-001

Covance Study ID: 000000203201

### 1. Source Documents

The Statistical Analysis Plan (SAP) was written based on the following documentation:

Document	Date	Version
Protocol	07 July 2021	4.0
eCRF	06 September 2021	3.06

**CONFIDENTIAL**

Document Date: 29 Nov 2021

Page 7 of 34  
ST-AD-008 version 05

## Statistical Analysis Plan

Sponsor Name: Golden Biotechnology Corporation  
Sponsor Protocol ID: GH Covid-2-001

Covance Study ID: 000000203201

## 2. Protocol Details

### 2.1 Study Objectives

The primary objectives of this study is:

- To evaluate the efficacy of antroquinonol treatment of mild to moderate pneumonia due to COVID-19, as measured by the proportion of patients alive and free of respiratory failure (i.e., no need for invasive mechanical ventilation, non-invasive ventilation, high-flow oxygen, or extracorporeal membrane oxygenation [ECMO]) on Day 14

Secondary objectives of this study are:

- To further evaluate the efficacy of antroquinonol compared with placebo in this patient population as measured by:
  - World Health Organization (WHO) COVID-19 Clinical Improvement Ordinal Scale score on Days 7, 14, and 28
  - Duration of hospitalization up to Day 28
  - Virological clearance on Days 5, 14, and 28
  - Vital status (death) on Days 7, 14, and 28
  - Duration of intensive care unit (ICU) stay up to Day 28
  - Proportion of patients alive and free of respiratory failure on Days 7 and 28
  - COVID-19 symptoms on Days 7, 14, and Day 28
- To evaluate the safety of antroquinonol treatment in patients with mild to moderate pneumonia due to COVID-19.
- To assess the pharmacokinetics (PK) of antroquinonol in a subset of 20 patients (first 10 patients randomized to antroquinonol and first 10 patients to placebo)

Exploratory objective of this study is:

- To further evaluate efficacy via supportive analyses of:
  - Subgroup analyses of selected covariates
  - Impact on efficacy of any new authorized treatments recommended as standard of care (SoC) for COVID-19 during the course of the study.

### 2.2 Overall Study Design

This is a randomized, double blind, placebo-controlled, Phase 2, proof of concept study in hospitalized patients with mild to moderate pneumonia due to COVID-19. Written informed consent must be obtained from all patients during screening (Days -2 to 0). Following completion of all screening assessments and meeting of eligibility criteria, patients will either receive antroquinonol or placebo for 14 days in combination with SoC therapy per local SoC policies.

**CONFIDENTIAL**

Document Date: 29 Nov 2021

Page 8 of 34  
ST-AD-008 version 05

## Statistical Analysis Plan

Sponsor Name: Golden Biotechnology Corporation

Sponsor Protocol ID: GH Covid-2-001

Covance Study ID: 000000203201

A total of 174 patients are planned to be randomized in a 1:1 ratio to antroquinonol or placebo.

The study will consist of a sentinel cohort of 20 patients (10 patients randomized to antroquinonol and 10 patients to placebo), and an expansion cohort of 154 patients (77 patients in each treatment group). Enrollment will pause after the 20th patient in the sentinel cohort has been enrolled and started treatment, until the results of the interim analysis 1 are known. Once the 20th patient in the sentinel cohort has completed 14 days of treatment, an unblinded Data Monitoring Committee (DMC) will assess the safety, tolerability, efficacy, and PK of 100 mg twice daily (BID) antroquinonol in COVID-19 patients in the sentinel cohort (interim analysis 1). The DMC will issue a recommendation to enroll patients for the expansion cohort, or to stop the study depending on the safety and futility assessment. Once the 80th patient has been enrolled, and completed 14 days of treatment, the DMC will review the safety, tolerability, and efficacy data (interim analysis 2). Enrollment may be restricted at the 100th patient until the DMC has completed the assessment to prevent excessive enrollment. The DMC will continue to review safety and assess the risk/benefit profile on an ongoing basis. A DMC Charter, which includes detailed processes, will be prepared.

Patients will undergo assessment during hospitalization or could be discharged after start of study treatment any time after Day 2 if judged to be ready for discharge. If discharged, patients will then be requested to take study treatment at home (as prescribed) up to Day 14. End of Treatment assessments at Day 14 (+2 days) (at home or site visit) will be performed. A Day 5 (+/- 1 day) visit (at home or site visit) will be performed if the patient is discharged prior to Day 5. If the patient is discharged after completion of treatment and before the follow-up visit, he/she will be followed up on Day 28 ( $\pm 2$  days) for study assessments (a telephone or telemedicine visit). Post discharge, assessments will be done by telephone or telemedicine, except for Day 5, Day 14, and Early Termination (ET) of Study Treatment. On days of laboratory assessments, discharged patients will have a home visit. On days of no laboratory assessments, discharged patients will complete their assessments via telephone, telemedicine, or other means of remote communication. Additionally, patients will receive a diary to capture all doses after a discharge.

### 2.3 Sample Size

A total of 174 patients are planned to be randomized into the study:

- 20 patients in the sentinel cohort (10 patients in each treatment group)
- 154 patients in the expansion cohort (77 patients in each treatment group).

This enrollment level ensures 80% power to demonstrate proof of concept efficacy with one-sided alpha of 0.2.

The sample size is based on the following assumptions:

- The randomized allocation ratio is 1:1 between the antroquinonol group and the placebo group
- The proportion of patients alive and free of respiratory failure is approximately 78% on placebo vs 89% on antroquinonol

**CONFIDENTIAL**

Document Date: 29 Nov 2021

Page 9 of 34

ST-AD-008 version 05

## Statistical Analysis Plan

Sponsor Name: Golden Biotechnology Corporation

Sponsor Protocol ID: GH Covid-2-001

Covance Study ID: 000000203201

- The following nonbinding rules will be considered by the DMC for futility, and the DMC will not make any recommendations to stop for early efficacy:
  - Interim analysis 1 (sentinel cohort): An odds ratio of 3.5 on the primary endpoint in favor of placebo.
  - Interim analysis 2: An odds ratio of 1.2 on the primary endpoint in favor of placebo. This analysis will be conducted on all data collected up to the 80th randomized patient completing 14 days of treatment. Enrollment may be restricted at the 100th patient until the DMC has completed the assessment to prevent excessive enrolment.

## 3. Efficacy and Safety Variables

### 3.1 Primary Efficacy Endpoint

The proportion of patients who are alive and free of respiratory failure (e.g., no need for invasive mechanical ventilation, non-invasive ventilation, high-flow oxygen, or ECMO) on Day 14.

### 3.2 Secondary Efficacy Endpoints

- Clinical improvement score as measured by the WHO COVID-19 Clinical Improvement Ordinal Scale, as follows:
  - Time to 2-point improvement from baseline.
  - Supportive analysis, time to score 2 or lower.
  - Supportive analysis, time to score 0.
- Duration of hospitalization (days) up to Day 28
- Virological clearance evaluated using PCR testing from nasopharyngeal or mid-turbinate samples on Day 5, 14, and 28:
  - Time to virological clearance, measured as study days from start of treatment to first negative SARS-CoV-2 PCR test
  - Rate of change in viral load will be evaluated depending on availability of quantitative assays.
- Vital status (death) on Days 7, 14, and 28
- Duration of ICU stay up to Day 28
- Proportion of patients alive and free of respiratory failure on Days 7 and 28
- COVID-19 symptoms on Days 7, 14, and 28. Assessment will evaluate: presence or absence of dry cough, dyspnea (shortness of breath/ difficulty in breathing), or chills/rigors, myalgia (muscle pain), headache, sore throat, and loss of taste or smell; other symptoms that could be related to COVID-19 will also be recorded.

## Statistical Analysis Plan

Sponsor Name: Golden Biotechnology Corporation  
Sponsor Protocol ID: GH Covid-2-001

Covance Study ID: 000000203201

### 3.3 Exploratory Efficacy Endpoint

To further evaluate the impact of the following parameters on the primary endpoint, the interaction term of treatment and following parameters will be fitted into the primary model one at a time.

- Age, sex, and remdesivir or other authorized treatments for COVID-19 use at baseline.
- Use of any new authorized treatments recommended as SoC for COVID-19 during the course of the study.

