4.4.2. Hepatic injury or renal impairment

4.4.2.1. *Hepatic injury*

Discontinuation of study treatment for abnormal liver tests should be considered by the investigator when a patient meets one of the conditions outlined in [Figure 2](#) or if the investigator believes that it is in the best interest of the patient.

Figure 2: Stopping Criteria for Liver Injury

Abbreviations: ALT = alanine aminotransferase; INR = international normalized ratio; ULN = upper limit of normal
 Note: INR value is not applicable to patients on anticoagulants.

4.4.2.2. *Renal impairment*

If a patient has renal impairment (creatinine clearance <50 mL/min), treatment should be discontinued.

4.4.3. **Discontinuation of study treatment**

A patient may be discontinued early from study drug treatment (ET of study treatment) for the following reasons:

- Lack of efficacy (e.g. patients who require nonstudy antiviral or anticytokine therapy due to progression of COVID-19), and the investigator's decision. Note: remdesivir or other authorized treatments for COVID-19 is allowed if considered SoC, if started prior to randomization or during the study. Initiation of remdesivir or other authorized treatments for COVID-19 during the study will be considered a treatment failure if started due to progression of disease.
- Adverse event
- Withdrawal by patient (specify reason in the eCRF)
- Lost to follow-up
- Death

- Physician decision (i.e. investigator decision based on protocol deviation, assessment that it is not in the patient's best interest to continue, or other reason [specify reason in the eCRF]).
- Sponsor decision (specify reason in the electronic case report form [eCRF])

No temporary treatment discontinuation is permitted.

Patients who discontinue study treatment prematurely will be asked about the reason(s) for discontinuation and will be asked to continue all assessments up to Day 28. Patients will be educated about the continued scientific importance of their data and encouraged to complete the Day 28 Follow-up/EOS assessments even if they discontinue study treatment prematurely.

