7.1.3. Exploratory efficacy endpoints

The exploratory efficacy endpoints include:

- Covariates of age, sex, and remdesivir or other authorized treatments for COVID-19 use at baseline
- Use of any new authorized treatments recommended as SoC for COVID-19 during the course of the study

The final list of covariates for subgroup analyses are as detailed in the final statistical analysis plan.

New authorized treatments to be analyzed will be identified post hoc and will be collected from the concomitant medications eCRF page.

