### **7.6.3 Exploratory Efficacy Analysis**

Subgroup analyses on primary endpoint will be provided for the parameters of age at baseline ( $> 65$  years vs  $\leq 65$  years), sex, and remdesivir or other authorized treatments for COVID-19 use at baseline. The interaction between each mentioned parameter and the treatment effect will be added one at a time into the primary logistic model and the corresponding p-value for that interaction term will be provided.

The impact on efficacy of any new authorized treatments recommended as SoC for COVID-19 during the course of the study will also be evaluated using the same method as above.

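### The exploratory analysis of new authorised treatments interacts randomised treatment with use that can begin after randomisation, so its stratum effects and interaction test are not protected by randomisation and can be biased in either direction

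*SAP*

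**What the plan says.** SAP 3.3 says that treatment-by-parameter interaction terms will be fitted into the primary model one at a time. Its first bullet lists age, sex and use of remdesivir or other authorised treatments, and ties that use to baseline. Its second bullet reads "Use of any new authorized treatments recommended as SoC for COVID-19 during the course of the study" and has no such tie. SAP 7.6.3 describes the subgroup and interaction analysis for the baseline factors and adds that the impact of the new treatments "will also be evaluated using the same method as above".

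Four other places determine what this variable contains:

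- Protocol 7.1.3: "New authorized treatments to be analyzed will be identified post hoc", with the data taken from the concomitant-medication page.
- SAP 7.5.2: concomitant medications include those started on or after the first dose, and those started earlier and still continuing.
- Protocol Appendix 5 and SAP Appendix 2, note i: concomitant medications are recorded to Day 28.
- Protocol 4.4.3 and 6.2: authorised treatments are allowed as standard of care before randomisation or during the study. Starting one on study "will be considered a treatment failure if started due to progression of disease".

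The objective served is exploratory (Protocol 2.1, SAP 2.1). No decision rule is attached to it.

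**The concern.** Age, sex and baseline use are fixed before treatment can act, so a subgroup comparison on them is still a randomised comparison. Use of a new treatment after randomisation is not fixed. If antroquinonol prevents progression, and progression prompts the new treatment, the two arms will have different kinds of patients among users and among non-users. Nothing in the plan confines the variable to the time before Day 14 either. A patient in respiratory failure on Day 12 who starts a new drug on Day 20 is classed as a user in a model of the Day 14 outcome.

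At stake is the stated question of whether the drug effect depends on new standard of care. An interaction can appear when the new treatment modifies nothing, and a real one can be hidden. The SAP attaches no caveat, although SAP 7.6.2.1 treats starting an authorised treatment not prescribed at baseline as a censoring event in one of its two time-to-event analyses.

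**Working it through.** **The plan's own figure.** SAP 2.3 states "This enrollment level ensures 80% power to demonstrate proof of concept efficacy with one-sided alpha of 0.2", with "The proportion of patients alive and free of respiratory failure is approximately 78% on placebo vs 89% on antroquinonol". Using 87 per arm:

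- The success odds ratio is (0.89/0.11)/(0.78/0.22) = 2.28, or 0.44 for failure.
- SE of the log odds ratio = √[(1/(0.78×0.22) + 1/(0.89×0.11))/87] = 0.429.
- Fixed-design Wald power = Φ(0.825/0.429 − 0.842) = 86.0%. The pooled two-proportion test gives 87.0%.
- With both futility rules followed (odds ratio 3.5 at 20 patients, 1.2 at 80), 400,000 simulated trials give 80.1% (binomial) or 81.1% (normal approximation).
- The final boundary is exp(−0.8416 × 0.429) = 0.697, as in Protocol 8.1.

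The stated 80% is reproduced. This calculation does not involve the exploratory interaction.

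**Progression-driven use.** All rates here are assumptions. Progression is 30% on placebo and 15% on drug. Failure is 70% after progression and 1.4% otherwise, whether or not the new treatment is used. The new treatment is given to 90% of progressors and 5% of others.

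- Failure: placebo 0.30×0.70 + 0.70×0.014 = 22.0%; drug 0.15×0.70 + 0.85×0.014 = 11.7%. Odds ratio 0.470.
- Use: placebo 0.27 + 0.035 = 30.5%; drug 0.135 + 0.0425 = 17.8%.
- Users: placebo (0.27×0.70 + 0.035×0.014)/0.305 = 62.1%; drug (0.135×0.70 + 0.0425×0.014)/0.1775 = 53.6%. Odds ratio 0.703.
- Non-users: placebo (0.03×0.70 + 0.665×0.014)/0.695 = 4.36%; drug (0.015×0.70 + 0.8075×0.014)/0.8225 = 2.65%. Odds ratio 0.597.

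The new treatment does nothing in this set-up, yet users and non-users differ by a ratio of 0.703/0.597 = 1.18.

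**Other mechanisms.** The table gives failure odds ratios, drug versus placebo. Rows A, B, F and G use the plan's 78% and 89%.

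| Assumed use | Overall | Users | Non-users | Ratio |
|---|---|---|---|---|
| A. 40% in both arms, whatever the course | 0.44 | 0.44 | 0.44 | 1.00 |
| B. 60% of failures, 10% of successes, both arms | 0.44 | 0.44 | 0.44 | 1.00 |
| C. Progression-driven, as above | 0.47 | 0.70 | 0.60 | 1.18 |
| D. As C, but all progressors and only they | 0.47 | 1.00 | 1.00 | 1.00 |
| E. As C, progressors who start it counted as failures | 0.43 | 0.41 | 0.60 | 0.69 |
| F. Failures 70% placebo, 50% drug; successes 10% | 0.44 | 0.31 | 0.73 | 0.43 |
| G. Failures 50% placebo, 70% drug; successes 10% | 0.44 | 0.61 | 0.26 | 2.33 |
| H. Strong unmeasured frailty, progression-driven | 0.82 | 0.99 | 1.54 | 0.64 |

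- Row E: users fail in (0.27 + 0.00049)/0.305 = 88.7% on placebo and (0.135 + 0.000595)/0.1775 = 76.4% on drug. Overall failure is 30.1% against 15.7%.
- Row F, users: (0.11×0.5)/(0.89×0.1) ÷ (0.22×0.7)/(0.78×0.1) = 0.618/1.974 = 0.31.
- Row H: half the patients are frail. The logit of progression is −2.5 + 4×frail − 1.5×drug, the logit of success is 3.5 − 3×frail − progression, and use is 95% of progressors and 5% of others.

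These are odds ratios from the treatment-by-use table without the age and baseline-use covariates. For a baseline factor, non-collapsibility alone would move stratum odds ratios away from 1, so it does not explain rows C and D.

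**Precision.** With 2% dropout, 174 × 0.98/2 ≈ 85 per arm. Take use as unrelated to outcome. The interaction variance is the sum of 1/[n p(1−p)] over the four cells. With 20% users the SE is 1.09, and with 40% it is 0.89. Power for an interaction odds ratio of 2 is then 9% to 12% at one-sided 0.025, and 42% to 48% at one-sided 0.2.

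**The case against.** The strongest reply is that the documents do not make use a response to progression. Patients receive standard of care under local policy. Authorised treatments may start before randomisation, and starting one because of progression is only a conditional case. The phrase about the course of the study may describe when the treatment was recommended rather than when it was used, and drugs continuing from before the first dose also count as concomitant. If policy alone drives use, row A applies and there is no bias. All of this stands, and it rules out presenting use as progression-driven in fact. It does not restore the randomised comparison, because nothing limits use to baseline and the protocol itself provides for starts due to progression.

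A reader might also infer that the drug effect is pulled toward the null in every stratum. That needs particular mechanisms such as C or D. It fails in A and B (no bias), in F and G (one stratum away from the null) and in H (non-users past it). In E, where the protocol's treatment-failure rule is applied to the inputs of C, users show 0.41 against 0.43 overall.

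It is also fair that the analysis is exploratory and weakly powered, that concomitant medications are already tabulated by arm, and that the time-to-event endpoints are analysed with and without censoring at new treatment. These points limit the consequence. They do not make the interaction interpretable.

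**Conclusion.** The concern holds in a limited form. Followed as written, SAP 3.3 and 7.6.3 stratify by a variable that treatment and progression may affect, with no cut-off at randomisation or at Day 14. The stratum effects and the interaction test are therefore not protected by randomisation, and the sign of any bias cannot be known in advance. In the assumed examples, a failure odds ratio of 0.44 to 0.47 overall corresponds to stratum values from 0.26 to 1.00. With no effect modification built in, the ratio between strata ranges from 0.43 to 2.33 (rows A to D, F and G). The use, progression and frailty rates are illustrative because the documents give none. The documents support neither a claim that use always follows progression nor a claim of uniform bias toward the null.

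The consequence is confined to one exploratory objective. The primary model adjusts only for baseline use and age, and the primary estimate, the 174 patients and the 80% power do not change.

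An adjacent gap should be settled separately. The protocol calls progression-driven initiation a treatment failure, but the SAP does not say whether it counts as failure in the Day 14 endpoint. The two must be reconciled.

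**What to change.** In SAP 3.3 and 7.6.3, replace on-study use with a moderator fixed at randomisation: whether the new treatment was authorised or recommended as standard of care in the patient's country or site on the randomisation date, or whether the patient was using it at baseline. Each within-stratum comparison then stays randomised. Report initiation after randomisation by arm, with start date and reason, descriptively as a post-randomisation outcome. Protocol 6.1 already collects dates and reason for use. The existing concomitant-medication summary does not separate new starts from continuing drugs, so this needs its own table.

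The cost is SAP wording, one table and a lookup of authorisation or recommendation dates. Country-level dates should be easier to establish than site-level availability, for which the documents describe no data. Calendar period may also carry other changes, such as the Protocol 4.0 requirement for oxygen saturation below 94%. The interaction should therefore be read as a period or availability effect, not as the effect of the new drug itself. If on-study use is kept in any form, label the result descriptive and non-causal, and state a time window that ends before the Day 14 outcome.
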